## 3.3 Study Subjects

### 3.3.1 Subject Disposition and Completion Status

Table 3.3.1-1 presents the summaries that will be prepared for subject disposition.

**Table 3.3.1-1 Subject Disposition to be Summarized**

Summary	Population
Number of Subjects Entered by Site	All subjects entered
Subject Status at the End of Treatment	As-treated
Subject Status at the End of Study	As-treated
Mortality Summary	As-treated

Summaries of the number and percentage of subjects entered at each site will be provided.

The summary of subject status at the end of study treatment will include the number and percentage of subjects who ended treatment due to any of the following reasons: completed protocol-defined end of treatment, adverse event (AE), progressive disease, death, lost to follow-up, protocol violation, subject decision, investigator decision, or other.

Subject status at the end of study will be summarized in terms of the number and percent of subjects who are classified as the following: completed, lost to follow-up, withdrawal by subject, death, or other. For the subjects who discontinue the study due to withdrawal of consent, the reason for withdrawal (AE or other) will be summarized.

The end of study mortality summary will include subjects who are dead at the end of study, the cause of death (due to disease vs not due to disease) and the relationship to investigational product (related vs. not related).

### 3.3.2 Demographics and Baseline Characteristics

Summaries of demographics and baseline characteristics will be provided for the As-treated population to describe the subject populations in this study. These summaries will aid in interpretation of the assessment of the primary and secondary objectives and provide an overview of study conduct. The summaries to be provided are listed in [Table 3.3.2-1](#).

**Table 3.3.2-1 Summaries of Baseline Characteristics**

Summary	Population
Demographics	As-treated
Disease History	As-treated
Prior Cancer Treatment	As-treated
Baseline Disease Status Assessment	As-treated
Baseline Tumor Characteristics	As-treated
Baseline ECOG Performance Status	As-treated
Smoking History	As-treated

ECOG = Eastern Cooperative Oncology Group.

Demographics will be summarized for the following characteristics: age (year), gender, height (cm), weight (kg), ethnicity, and race.

The disease history summary will include frequency distributions for disease stage at initial diagnosis (IA, IB, IIA, IIB, IIIA, IIIB, IV, unknown), tumor stage at initial diagnosis (T0, Tis, T1, T2, T3, T4, TX, unknown), node stage at initial diagnosis (N0, N1, N2, N3, NX, unknown), metastasis stage at initial diagnosis (M0, M1, MX, unknown), histologic type

(carcinoma, adenocarcinoma), and descriptive statistics of time from primary diagnosis to study entry (months). Mutation will be provided in listing and will be summarized by mutation type. (e.g. Exon 18 Gly719#, Exon 20 insertion, etc).

Prior cancer treatment will be summarized by using the number and percentage of subjects who have received each of the following therapy categories: systemic therapy, radiation, cancer related surgery, or other. Previous lines of therapy will be summarized. Best response of prior cancer treatment will be summarized by the following categories: complete response (CR), partial response (PR), stable disease (SD), progressive disease (PD), not evaluable, not applicable and unknown. Descriptive statistics of number of prior treatment regimens will be provided.

Baseline disease status assessment summary will include frequency distributions for disease stage at study entry (IA, IB, IIA, IIB, IIIA, IIIB, IV), tumor stage at study entry (T0, Tis, T1, T2, T3, T4, TX, unknown), node stage at study entry (N0, N1, N2, N3, NX, unknown), metastasis stage at study entry (M0, M1, MX, unknown) and T790M status determined by a central lab (negative, positive) when available.

Baseline tumor characteristics including number and sites of target tumor lesions and number and sites of non-target tumor lesions will be summarized. The size of baseline target lesions will also be summarized in terms of sum of the measurement of measurable target lesions using descriptive statistics.

Baseline Eastern Cooperative Oncology Group (ECOG) performance status will be summarized using frequency distributions for the collected categories.

Smoking history will be summarized.

### 3.3.3 Study Drug Exposure

The summaries of exposure to each IP to be provided are listed in [Table 3.3.3-1](#).

**Table 3.3.3-1 Study Drug Exposure**

Summary	Population
Study Treatment Exposure	As-treated
Dosing Delay of Investigational Products	As-treated
Summary of Subsequent Alternative Cancer Treatment	As-treated

Summary of study treatment exposure will include descriptive statistics of the following: total duration of exposure in months, total number of IP doses, total dose received during the study, dose intensity and relative dose intensity. Dose intensity and relative dose intensity to IP(s) will be summarized by descriptive statistics.

The duration of exposure for oleclumab is defined as last dose date + 14 days minus first dose date for subjects on treatment or minimum of (date of death plus 1 day, data cutoff date plus 1 day, or last dose date + 14 days) minus first dose date for subjects who discontinued treatment. The duration of exposure for Osimertinib or AZD4635 is defined as last dose date + 1 days minus first dose date. The relative dose intensity is a percent of total actual dose that a subject received during corresponding study treatment period versus the total intended dose for the same study treatment period according to the study protocol. The details of the dose intensity calculation will be provided in the SPP as part of the standard exposure TFL templates.

Dosing deviations for IP(s) will be summarized with reasons for deviations for the following categories: delays, omissions, reductions, and interruptions. Dosing delays will be derived based on the scheduled dosing dates. The number of subjects with dosing delays and total dose delays will be summarized.

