**Figure 2.1.3-1 Study Flow Diagram for Part 1: Dose Escalation**

EGFRm = epidermal growth factor receptor mutant; EGFR TKI = epidermal growth factor receptor tyrosine kinase inhibitor; IV = intravenously; N = number; NSCLC = non-small cell lung cancer; PO = orally; Q2W = every 2 weeks; QD = once daily.

**NOTE:** For both Arms A and Arm B, subjects must have received treatment with an approved first or second generation EGFR TKI except for subjects in Arm B who received osimertinib as first-line treatment, in which case, treatment with a first or second generation EGFR TKI is not required, and these subjects may enroll after having received and progressed on osimertinib alone (but can still have received no more than 4 prior lines of therapy).

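### SAP Section 3.3.3 caps oleclumab exposure at the data cutoff only for discontinued subjects, so ongoing subjects can be credited with up to 13 days beyond it

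*SAP*

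**What the plan says.** SAP Section 3.3.3 lists "total duration of exposure in months" among the exposure summaries, all on the as-treated population, and then defines duration separately for each product.

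- **Oleclumab, ongoing subjects:** duration "is defined as last dose date + 14 days minus first dose date for subjects on treatment".
- **Oleclumab, discontinued subjects:** duration is the "minimum of (date of death plus 1 day, data cutoff date plus 1 day, or last dose date + 14 days) minus first dose date". The group is named at the end of that clause: "minus first dose date for subjects who discontinued treatment".
- **Oral partners:** "The duration of exposure for Osimertinib or AZD4635 is defined as last dose date + 1 days minus first dose date".

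The notes to the study flow diagrams (Figures 2.1.3-1 and 2.1.3-2) give the interval abbreviation "Q2W = every 2 weeks". This agrees with the 14 days in the oleclumab formula and with the third oleclumab dose at Day 28 in the definition of the DLT-evaluable population (Table 3.2-1).

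No other section of the SAP limits the ongoing-subject formula. Section 3.3.3 leaves the details of dose intensity to the SPP, but it does not leave the duration of exposure there.

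**The concern.** The plan includes a cutoff limit, so its authors evidently meant to keep reported exposure from running past the data available. The limit is attached to the group in which it seldom matters. A discontinued subject is affected only if the last dose fell within 12 days before the cutoff. An ongoing subject on a two-week schedule will normally have had the last dose within that span, so the limit would usually bind.

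As a result, two subjects with the same first dose, last dose and cutoff dates can be given durations up to 13 days apart, solely because one is recorded as discontinued. The SAP gives no reason for this. At stake is the accuracy and internal consistency of a reported exposure figure at any cutoff with subjects still on oleclumab. The relative effect is largest when follow-up is short.

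**Working it through.** The SAP states no exposure figure to reproduce, so the check is day arithmetic on its two formulas.

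**Inputs**

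- F = first dose date, L = last dose date, C = data cutoff date.
- k = C − L, the days from last dose to cutoff (k ≥ 0).
- Ongoing formula (Section 3.3.3): L + 14 − F.
- Discontinued formula (Section 3.3.3), for a subject alive at cutoff: min(C + 1, L + 14) − F.
- Dosing interval: 14 days.
- Month length: 365.25/12 = 30.4375 days. The SAP uses this conversion for PFS, DOR and OS. Its use for exposure is assumed here.

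**Step 1: excess for one ongoing subject.**
Excess = (L + 14) − min(C + 1, L + 14). With L = C − k this is max(0, 13 − k) days.

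| k (days from last dose to cutoff) | Excess (days) |
|---|---|
| 0 | 13 |
| 7 | 6 |
| 12 | 1 |
| 13 or more | 0 |

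The maximum is 13 days, and 13/30.4375 = 0.43 month.

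**Step 2: where the cap binds.**
L + 14 exceeds C + 1 only when k < 13. For an on-schedule ongoing subject k lies between 0 and 13, so the cap would bind at 13 of the 14 possible values.

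**Step 3: mean per ongoing subject.**
Assume k is spread evenly over 0 to 13. The mean excess is (13 + 12 + … + 0)/14 = 91/14 = 6.5 days, and 6.5/30.4375 = 0.21 month.

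**Step 4: shift in the arm mean.**
Shift = 6.5 × fraction of the arm still on oleclumab at the cutoff. The SAP does not give this fraction, so a range is shown:

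- 10% ongoing: 6.5 × 0.10 = 0.65 day
- 50% ongoing: 6.5 × 0.50 = 3.25, about 3.3 days
- none ongoing: 0

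**Step 5: worst case by number of on-schedule doses, with the last dose on the cutoff date (k = 0).**
Uncapped duration is 14 × doses. Capped duration is 14 × (doses − 1) + 1.

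| Doses | As written for ongoing subjects (days) | Capped (days) |
|---|---|---|
| 1 | 14 | 1 |
| 6 | 84 | 71 |
| 26 | 364 | 351 |

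The absolute difference is always 13 days, so its relative weight is greatest early in treatment.

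**Step 6: effect of the cap on dose intensity, if the SPP were to divide by this duration (an assumption).**
Six on-schedule doses cover 6 × 14 = 84 planned days. Dividing by the capped 71 days gives 84/71 = 118%. The denominator therefore has to be fixed separately from the reported duration.

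**The case against.** The best defence is that crediting an ongoing subject with the full interval covered by the last dose is a legitimate convention, and that it keeps an on-schedule subject at 100% if duration also serves as the dose-intensity denominator. On this view nothing is miscalculated and the plan is merely asymmetric.

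Part of this stands. The point is an inconsistent definition, not a wrong sum, and Step 6 shows that a cap applied carelessly could distort dose intensity. But the convention does not explain why the cutoff term is present for discontinued subjects and absent for ongoing ones. The dose-intensity worry depends on the SPP, which is not at hand. It can be met there, because Section 3.3.3 already leaves those details to it.

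Two stronger readings are tempting, and the document supports neither.

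- **That oleclumab is treated inconsistently with osimertinib and AZD4635.** It is not. Adding 14 days for a drug given every two weeks and 1 day for a daily drug is the same convention: last dose plus one dosing interval.
- **That the extra days bias the adverse-event results.** The SAP plans no exposure-adjusted event rate. Section 3.6.2 counts each subject once per term and sets its own window of 28 days after the last dose. The ILD monitoring in Section 3.9 works from cases against subjects enrolled.

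**Conclusion.** The point holds as a minor inconsistency. Followed literally, Section 3.3.3 credits ongoing subjects with 0 to 13 days of oleclumab exposure after the data cutoff, at most 0.43 month each, while discontinued subjects with identical dates are capped. The range follows directly from the two formulas. The 6.5-day mean depends on evenly spread last doses, and the effect on an arm mean depends on the fraction ongoing, which the SAP does not give. The effect shrinks towards zero as subjects come off treatment.

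Only the descriptive exposure summaries are affected. No definition of ORR, DCR, DOR, PFS or OS uses this duration, and neither do the ILD thresholds or any interim rule visible in the SAP. Carry-over into dose intensity is possible, but the SAP does not state it.

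**What to change.** In Section 3.3.3, replace the two oleclumab formulas with one for the reported duration in all subjects:

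min(last dose date + 14, date of death + 1, data cutoff date + 1) − first dose date.

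In the SPP, state that the dose-intensity denominator is the planned dosing period and not this capped duration, so that an on-schedule ongoing subject is not shown above 100%.

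The cost is one line in the SAP, one in the SPP and one in the exposure program. Mean reported oleclumab exposure falls slightly at any cutoff with subjects still on treatment. No other definition in the SAP needs to change.

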### **3.3.4 Concomitant Medications**

The number and percentage of subjects who took at least 1 dose of medication other than investigational product during the study (concurrent medications) will be summarized by the generic name coded by World Health Organization (WHO) dictionary. The summary table of concomitant medications will include all concomitant medications taken on or after the date of first dose of investigational product or any concomitant medication started prior to first dose of study treatment that continued beyond the date of first dose of investigational product.

## **3.4 Efficacy Analyses**

### **3.4.1 Primary Efficacy Endpoint(s) and Analyses**

#### **3.4.1.1 Primary Efficacy Endpoint(s) and Analysis**

The primary efficacy endpoint is objective response per RECIST 1.1 by investigator assessment. Objective response rate (ORR) is defined as the proportion of subjects with a best overall response of confirmed CR or confirmed PR that occur prior to the initiation of

subsequent anticancer treatment. The rules for confirmation of CR or PR are the same as described in Section 3.4.2.1. The primary analysis of ORR will be based on the as-treated population in Part 2 (including subjects dosed at the RP2D in Part 1). ORR will be estimated with a 95% CI using the exact binomial distribution. Subjects that have missing best overall response assessments will be considered non-responders, and will therefore be counted in the denominator, but not in the numerator of ORR. In addition, above analysis may also be performed based on the response -evaluable population in Part 2 (including subjects dosed at the RP2D in Part 1).

### **3.4.2 Secondary Efficacy Endpoint(s) and Analyses**

The secondary efficacy endpoints include best overall response (BOR); duration of response (DOR); progression-free survival (PFS); overall survival (OS); disease control (DC). The efficacy endpoints will be summarized based on the as-treated population. Additional summaries based on the response--evaluable population may be presented.

Efficacy analyses, except for OS, will be based on an application of Response Evaluation Criteria in Solid Tumors (RECIST) 1.1 (Eisenhauer et al, 2009) to investigator assessed tumor measurements.

The Investigator assessed Response per RECIST 1.1 will be programmatically derived based on the investigator reported target, non-target, and new lesions assessments. [Appendix 7.1](#) provides the derivation rules.

#### **3.4.2.1 Best Overall Response**

Best overall response is defined as the best response (in the order of CR, PR, SD, PD, and not evaluable) among all overall responses recorded from the start of treatment with investigational product until objective documentation of PD, or the last evaluable disease assessment in the absence of PD prior to the initiation of subsequent anticancer therapy or end of the study, whichever occurs first. Best overall response (BOR) will be programmatically derived based on all post-baseline disease assessments that occur prior to the initiation of subsequent anticancer treatment. BOR will be summarized with the number and percentage of subjects for the following categories: CR; PR; SD; PD; and non-evaluable (NE). At least 8 weeks [-3 days] from the first dose of investigational product must elapse without a subsequent radiological disease progression in order to assign a best overall response of SD. The definition of 54 days will allow for the protocol-defined disease assessment window of 8 weeks ( $57 \pm 3$  days) for the first post dose disease assessment.

Confirmation of CR and PR is required and must occur no fewer than 4 weeks after initial documentation of CR or PR. If CR is pending confirmation and is designated at an assessment followed by 1 or more NE assessments, and/or PR assessments such that a) the Target Lesion Response is CR and the Non-Target Lesion Response is NE, or b) the Target Lesion Response is PR due solely to an increase in one or more lymph nodes to a size  $\geq 10$  mm and the Non-Target Lesion Response is either CR or NE, CR may be confirmed thereafter. Similarly, if a PR is pending confirmation and is designated at an assessment followed by 1 or more NE and/or SD assessments, PR may be confirmed thereafter.

In general, subjects not classifiable under the RECIST 1.1 response categories due to insufficient data or early death will be classified as non-evaluable for BOR, but will be counted in the denominator of all response rate calculations. This generalization includes if a subject has missing lesion data at baseline. In this scenario, the subject will be classified as non-evaluable for BOR. If a subject is missing lesion data at a disease assessment and yet progressive disease criteria is met despite the missing data, the subject will be classified as PD.

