### 7.1.2 Non-Target Lesion Response

Non-target lesion response will be assigned by site personnel following a qualitative overall assessment of all non-target lesions.

Possible values include:

- CR – Complete Response

- Disappearance of all non-target lesions and normalization of tumor marker level. All lymph nodes must be non-pathological in size (<10mm short axis)
- Non-CR/Non-PD – Non-Complete Response / Non-Progressive Disease
  - Persistence of one or more non-target lesion(s) and/or maintenance of tumor marker level above the normal limits
- PD – Progressive Disease
  - Unequivocal progression of existing non-target lesions.
- NE – Non-evaluable
- NA – Not Applicable (*set value for all post-baseline disease assessments only if no non-target lesions are identified at baseline*)

Though non-target lesion responses are a subjective decision made by the site personnel, certain responses may be limited depending on the non-target lesion statuses recorded. An algorithm is provided below highlighting appropriate possible non-target lesion responses based on recorded data. Reaching a red box (■) signifies having reached the only allowable non-target lesion responses based on non-target lesion statuses. Reaching a green box (■) signifies having reached the end of the algorithm and more than one possible non-target lesion response is possible from which the Investigator may choose.

1. a) If no non-target lesions are identified at baseline, all post-baseline non-target lesion responses should equal NA. ■  
b) Else, if any non-target lesions are identified at baseline, responses may be limited to CR, Non-CR/Non-PD, PD, NE (ie, responses of NA are not permitted).  

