### **7.1.3 Visit Disease Response per RECIST1.1**

Investigator visit disease response will be programmatically derived on the data collection instrument using RECIST 1.1 criteria based upon target lesion response, non-target lesion response, and new lesion data. Missing values in any of target lesion response, non-target lesion response, and new lesion data will result in the disease response not being derived.

Possible values include:

- CR – Complete Response

- PR – Partial Response
- SD – Stable Disease
- PD – Progressive Disease
- NE – Non-evaluable

Target Lesion Response	Non-Target Lesion Response	New Lesion	Derived RECIST Disease Response
CR	CR or NA	No	CR
CR	Non-CR/Non-PD or NE	No (or NE)	PR
PR	CR or Non-CR/Non-PD or NE or NA	No (or NE)	PR
SD	CR or Non-CR/Non-PD or NE or NA	No (or NE)	SD
PD	Any	Any	PD
Any	PD	Any	PD
Any	Any	Yes	PD
NE	CR or Non-CR/Non-PD or NE or NA	No	NE
NA	CR	No	CR
NA	Non-CR/Non-PD	No	SD (Non-CR/Non-PD) a
NA	NE or NA	No (or NE)	NE
NA	CR or Non-CR/Non-PD	NE	SD (Non-CR/Non-PD) a

a Per RECIST 1.1, “SD (Non-CR/Non-PD)” is preferred over “SD” for non-target disease since SD is increasingly used as endpoint for assessment of efficacy in some trials so to assign this category when no lesions can be measured is not advised.

If a subject has a missing tumor measurement at some assessment(s) for 1 or more target lesions and criteria for PD are not otherwise met, an overall response of NE will be assigned for the assessment(s).

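### The CR-confirmation rule in SAP 3.4.2.1 omits non-target NA, so a subject with no non-target lesions cannot have a CR confirmed across an intervening nodal PR

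*SAP*

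**What the plan says.** SAP Section 3.4.2.1 (Best Overall Response) sets the general requirement: "Confirmation of CR and PR is required and must occur no fewer than 4 weeks after initial documentation of CR or PR". It then allows a pending CR to be confirmed later when PR visits intervene, in two situations:

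- Clause (a): "the Target Lesion Response is CR and the Non-Target Lesion Response is NE".
- Clause (b): the target response has slipped to PR only because a node has regrown. The operative words are "increase in one or more lymph nodes to a size $\geq 10$ mm and the Non-Target Lesion Response is either CR or NE, CR may", and the sentence ends by allowing confirmation at a later visit.

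Two appendix sections decide which non-target values can occur:

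- Section 7.1.2, Rule 1a: "If no non-target lesions are identified at baseline, all post-baseline non-target lesion responses should equal NA". Rule 1b covers everyone else: "if any non-target lesions are identified at baseline, responses may be limited to CR, Non-CR/Non-PD, PD, NE (ie, responses of NA are not permitted".
- Section 7.1.3 (visit response table): with no new lesion, target CR together with non-target CR or NA gives a visit CR. For target PR, the accepted non-target values are "CR or Non-CR/Non-PD or NE or NA", and the visit is PR.

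Sections 3.4.2 and 3.4.2.1 say that the RECIST response and the best overall response (BOR) are derived by program.

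**The concern.** NA is not an occasional data state. Under Section 7.1.2 it is the permanent non-target value for one defined group, the subjects with no non-target lesions at baseline, and nobody else can have it. Because clause (b) accepts only CR or NE, this whole group is shut out of it.

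The omission has no visible rationale. Leaving out Non-CR/Non-PD makes sense, because non-target disease then persists. That reason cannot apply to a subject with no non-target disease. The clause accepts NE, where non-target status is unknown, and refuses NA, where there is nothing to assess.

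Clause (a) does not need NA, because target CR with NA is already a visit CR in Section 7.1.3. Clause (b) does need it.

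At stake is the reported split between CR and PR in the BOR table. Two subjects with identical target-lesion courses can be placed in different categories because of a value that carries no information about disease.

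**Working it through.** The SAP gives no figure on this point to reproduce. The check is whether its own algorithms can reach the omitted state, and what clause (b) then does.

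**Inputs**

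- Target-lesion algorithm (7.1.1). PD needs a rise from nadir of at least 20% and at least 5 mm. CR needs non-nodal total 0 and every node below 10 mm. PR needs a change from baseline of -30% or lower.
- Visit table (7.1.3) and clause (b) (3.4.2.1), as set out above.
- Scans every 8 weeks, from the 8-week first assessment (3.4.2.1) and the 16 weeks given for two assessments (3.4.2.4).
- Illustrative assumption: baseline non-nodal lesion 40 mm plus node 20 mm, sum 60 mm, no new lesions.

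**Target response**

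1. Week 8: non-nodal 0, node 8 mm. The node is below 10 mm, so target CR. The nadir is now 8 mm.
2. Week 16: non-nodal 0, node 11 mm. Rise from nadir = 11 - 8 = 3 mm, or 3/8 = 37.5%. The 20% condition is met but the 5 mm condition is not, so this is not PD. The node is not below 10 mm, so it is not CR. Change from baseline = (11 - 60)/60 = -81.7%, so target PR, due solely to the node.
3. Week 24: node back to 8 mm, so target CR.

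Intervening node sizes of 10, 12 and 12.9 mm give the same CR, PR, CR series. At 13 mm the rise is 13 - 8 = 5 mm (62.5%), and the visit is PD. With an 8 mm nadir, the state is therefore reachable for a node from 10 mm to just under 13 mm.

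**Visit response and clause (b)**

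The non-target response is NA throughout for the subject without non-target lesions. For the other rows it is CR at Weeks 8 and 24, with the Week 16 value shown.

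| Non-target response at Week 16 | Visit responses | Week 8 CR confirmable as written | With NA added |
|---|---|---|---|
| CR | CR, PR, CR | yes | yes |
| NE | CR, PR, CR | yes | yes |
| NA | CR, PR, CR | no | yes |
| Non-CR/Non-PD | CR, PR, CR | no | no |

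The visit series is the same in all four rows. Adding NA changes only the NA row.

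**What the NA subject is reported as**

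- The Week 16 PR is followed 8 weeks later by a CR. On the natural reading, a later response at least as good confirms a PR, so BOR is confirmed PR.
- If a further CR is seen at least 4 weeks after Week 24, for example at Week 32, the Week 24 and Week 32 visits form a confirmed CR without any use of clause (b).

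**Size per subject**

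- Arm A: 1/46 = 2.2 percentage points of the CR category.
- Arm B: 1/52 = 1.9 percentage points.
- 46 and 52 are approximate enrolment ceilings (Section 2.4). In a smaller analysis set, each subject weighs more.

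**The case against.** The strongest case on the other side is that little follows from the omission.

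- *A reader might infer that the primary endpoint moves.* The documents do not support this. ORR counts confirmed CR or confirmed PR (3.4.1.1), and the subject in the example is still a confirmed PR. DCR (3.4.2.2) counts both as well. This objection stands.
- *A reader might infer that the subject is held at PR for good.* That is not so: a later CR at least 4 weeks after the second one restores a confirmed CR. This stands.
- *A reader might infer that DOR onset slips by one scan interval*, 56/(365.25/12) = 1.84 months. Section 3.4.2.3 starts DOR at the first documentation of a response that is later confirmed. A Week 8 CR followed by a Week 16 PR can be read as a response first documented at Week 8, with no shift. The SAP does not say how an unconfirmed CR followed by PR is dated, so the shift is possible but not established. That is a separate gap.
- *A reader might call clause (b) a contradiction of the visit table.* The table derives one visit and the clause works across visits, so no input gives two conflicting outputs. It is an omitted value.
- *A reader might conclude that subjects with more disease are favoured in general.* Only those with non-target CR, or NE at the intervening visit, are favoured. Subjects with Non-CR/Non-PD are excluded too.
- *A programmer might treat NA as CR*, since the visit table does so for target CR and clause (b) is worded permissively. This is only partly persuasive. The visit table names NA wherever it is allowed, so its absence from clause (b) reads as exclusion. Nothing in the SAP maps NA to CR for confirmation.

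**Conclusion.** The point holds as a small error in a stated rule. Followed literally, clause (b) denies confirmation of a CR across an intervening nodal PR to every subject without baseline non-target lesions, and it allows this to subjects with the same target course whose non-target response is CR, or NE at that visit.

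The consequence is limited to the CR/PR split of BOR: about 2 percentage points per affected subject if the arms reach 46 and 52. It should be rare. It needs no baseline non-target lesions, a visit CR, a nodal-only rebound that stays below the PD threshold, a return to CR, and no later CR that confirms the second one. The SAP gives no basis for a count of such subjects.

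ORR and DCR are not expected to change. That rests on reading a PR followed by a CR at least 4 weeks later as a confirmed PR. No effect on DOR is claimed.

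**What to change.** In SAP Section 3.4.2.1, clause (b), extend the accepted non-target values from CR or NE to CR, NE or NA. Clause (a) needs no change.

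The cost is one added value in the text and one in the BOR program. No new data are needed, and results for non-target CR, NE and Non-CR/Non-PD stay as they are. The study is open-label, so this is better settled in the SAP than by a programmer's reading once such a case has been seen.
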